7.3 Excluded Medications and Treatments

Subjects or parents/legal guardians will be instructed not to change a dose of current medication or begin taking any new medications, including over-the-counter products, without first consulting the investigator. Results of the urine alcohol and drug screen performed at Visit 9 must be negative for the subject to continue in the study.

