12. The subject is suffering from uncorrected coarctation of the aorta, or hemodynamically significant left ventricular outflow tract obstruction due to eg, aortic valvular disease, or is likely to undergo a procedure known to affect blood pressure (eg, repair of arterial anomalies) during the course of the study.
13. The subject has a history and/or presence of a clinically significant abnormal 12-lead ECG that is not related to medical history and/or concomitant diseases and is indicative of an unstable condition as determined by the investigator or sponsor/designee.
14. The subject is poorly controlled diabetic defined as having a glycosylated hemoglobin (HbA1c) value >8.5% at Screening/Visit 1.
15. The subject has alanine aminotransferase (ALT) or aspartate aminotransferase (AST) ≥2.5 times the upper limit of normal, or total bilirubin ≥1.5 times the upper limit of normal, severe hepatic impairment, active liver disease of any etiology, or jaundice at Screening/Visit 1 (exception may be made for subjects with Gilbert's disease, as long as subjects do not have active symptoms, such as indicated above).
16. The subject has hyperkalemia as defined by the central laboratory's normal reference range or any pertinent electrolyte disorders at Screening/Visit 1.

17. The subject has a known history of hepatitis B, hepatitis C or human immunodeficiency virus infection at Screening.
18. The subject has a known hypersensitivity or allergy to any angiotensin type II receptor blockers or to any of the excipients in AZM or losartan formulations to be taken
19. The subject has a history of drug or alcohol abuse within 1 year prior to Screening/Visit 1 or positive urine drug/alcohol screen test result at Screening/Visit 1. Subjects ≥ 12 years of age or younger children if deemed necessary by the investigator and their parents/legal guardians are required to give consent to urine alcohol/drug screen testing to be considered for eligibility. Subjects who have a positive drug screen for known physician prescribed medications (e.g. amphetamines for ADHD), are not abusing the medication in the investigator's judgment and are not an excluded medication are eligible for the study.
20. The subject has taken or requires the use of any medications or supplements within the stated time periods that are excluded, unable to washout excluded medications or not on a stable dose as described in the Excluded Medications or Concomitant Medications sections of this protocol.

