7.3.1 Washout/Placebo Run-in, Double-Blind and Withdrawal Phases: Excluded Medications

The following medications will be prohibited during the Washout/Run-in, DB and Withdrawal Phases. When appropriate, medications may be tapered-off gradually before double-blind treatment is initiated, but a minimum drug-free period of at least 7 days is required before randomization.

- All classes of antihypertensive drugs, including drugs that have an effect on BP but are prescribed for another indication, with the exception of concomitant medications listed in [Section 7.3.2](#).
- Lithium.
- Monoamine oxidase inhibitors.
- Tricyclic antidepressants.
- Amphetamines or their derivatives (see [Section 7.3.2](#) for exceptions).
- Dopamine agonists.

- Atypical antipsychotic agents.
- Anticonvulsants.
- Trazodone.
- Nitrates.

7.3.2 Washout/Placebo Run-in, Double-Blind and Withdrawal Phases: Concomitant Medications Allowed Conditionally

Conditional use of the following medications will be allowed in the Washout/Run-in, DB and Withdrawal Phases. These medications must be at a stable dose through the Week 8 visit (end of withdrawal phase) without changes unless absolutely medically necessary. Routine weaning and/or dose adjustments can be made during the open-label phase of the study:

- Diuretics, including loop-diuretics (eg, furosemide): Stable dose allowed if indicated for the treatment of oedema/CKD.
- Steroids: Systemic use is allowed at stable low/maintenance dose up to hydrocortisone 12 mg/m²/day (or the appropriate dose equivalent if other steroid is administered) for replacement therapy in subjects with adrenal insufficiency or other medical conditions. Immunosuppressive treatment in post renal transplant subjects or in subjects with glomerular disease with prednisolone is allowed at a maximum dose of 15 mg/m² (0.5 mg/kg) (or the appropriate dose equivalent if other steroid is administered). Doses need to be stable at least 30 days prior to Screening as mandated by inclusion criterion #8Topical and inhaled corticosteroids (eg, for treatment of asthma) are also allowed at stable maintenance doses.
- Central nervous system (CNS) stimulants: Stable dose allowed if indicated for treatment of attention deficit hyperactivity disorder.

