7.3.3 Open-Label Phase: Excluded Medications

The following medications are excluded during the OL Phase of the study.

- ARBs other than AZM.
- ACE inhibitors.
- Aliskiren.
- Chronic use of NSAIDs (ie, more than 3 times per week).

CONFIDENTIAL

- Lithium.
- Monoamine oxidase inhibitors.
- Nitrates.

Results of the urine alcohol and drug screen performed at Visit 9 must be negative for the subject to continue in the study.

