9.1.8 Procedures for Clinical Laboratory Samples

All samples will be collected in accordance with acceptable laboratory procedures. The maximum volume of blood at any single visit is approximately 11.5 mL, and the approximate total volume of blood for the study is 59 mL. Details of these procedures and required safety monitoring will be given in the laboratory manual.

Table 9.a Clinical Laboratory Tests

Hematology	Serum Chemistry	Urinalysis
RBCs	HbA1c for diabetic subjects only (a)	Creatine kinase
WBCs (with differential)	ALT	Cystatin C (b)
Hemoglobin	Albumin	eGFR by the Schwartz formula [45] (b)
Hematocrit	Alkaline phosphatase	γ -Glutamyl transferase
Platelets	AST	Glucose
Mean Corpuscular Volume (MCV)	Bicarbonate	Lipid panel (total cholesterol, LDL-C, HDL-C, and triglycerides)
Mean Corpuscular Haemoglobin (MCH)	Bilirubin (total, if increased measure direct)	Phosphate
Mean Corpuscular Haemoglobin Concentration (MCHC)	BUN (b)	Potassium (b)
Red Cell Distribution Width (RDW)	Calcium	Sodium (b)
	Chloride (b)	Total protein
	Creatinine (b)	

Other:**Blood**

Serum hCG (c): Only female subjects \geq 12 years old and younger females deemed to be of reproductive potential.
Pharmacokinetics sample (d)

Urine

Urine hCG (e): Only female subjects \geq 12 years old and younger females deemed by the principal investigator to be of reproductive potential.
Drug and alcohol screens (f): Only subjects \geq 12 years of age; however, testing may be completed for younger subjects if deemed appropriate by the principal investigator.

hCG=human chorionic gonadotropin, HDL-C=high-density lipoprotein cholesterol, LDL-C=low-density lipoprotein cholesterol, RBC=red blood cell, WBC=white blood cell.

(a) Screening/Visit 1, Week 8/Visit 9, Week 20/Visit 11, Week 36/Visit 13 and Week 52/Visit 16.

(b) Lab is part of the renal subpanel. The renal subpanel will be completed at Week 4/Visit 6 instead of the full clinical laboratory testing. The renal subpanel may also be requested by the investigator at unscheduled visits after study drug is titrated.

(c) Screening only.

(d) Collected on Day 1/Visit 4, Week 4/Visit 6, and Week 6/Visit 8.

(e) At all visits.

(f) Screening/Visit 1 and Week 8/Visit 9.

The central laboratory will perform laboratory tests for hematology, serum chemistries, urinalysis, lipid panel and other safety tests.

eGFR will be calculated by the central laboratory using the Schwartz formula [42].

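### Read literally, the Visit 9 drug-screen rule could remove a child taking a permitted ADHD stimulant, because it does not carry over the exception for prescribed drugs in exclusion criterion 19

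*Protocol*

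**What the plan says.** The urine alcohol and drug screen is done twice, as Table 9.a shows: "f) Screening/Visit 1 and Week 8/Visit 9". It is mandatory from age 12 and at the investigator's discretion below that.

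**The continuation rule.** Section 7.3 says: "Results of the urine alcohol and drug screen performed at Visit 9 must be negative for the subject to continue in the study". Section 7.3.3, on the open-label phase, repeats it: "Results of the urine alcohol and drug screen performed at Visit 9 must be negative". The Visit 9 procedure list in Section 9.3.5 and note (s) to Table 9.b carry the same requirement. Note (s) is attached to the urine-screen row as a whole, so it covers both screens.

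**The exception.** Exclusion criterion 19 in Section 7.2 tolerates some positive results: "Subjects who have a positive drug screen for known physician prescribed medications (e.g. amphetamines for ADHD"). The sentence adds the condition that the investigator judges the drug is not being abused, and ends "and are not an excluded medication are eligible for the study".

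**The permitted drugs.** Section 7.3.1 bars amphetamines but points to Section 7.3.2 for exceptions. For CNS stimulants, Section 7.3.2 says: "Stable dose allowed if indicated for treatment of attention deficit hyperactivity disorder". On the conditionally allowed drugs as a group it says "These medications must be at a stable dose through the Week 8 visit (end of withdrawal phase"), and then: "Routine weaning and/or dose adjustments can be made during the open-label phase of the study".

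**The concern.** The exception sits among the entry criteria and is worded as eligibility. The Visit 9 rule concerns continuation, is worded without qualification, and does not refer back to criterion 19. A child can therefore enter lawfully on a prescribed ADHD stimulant, hold the dose through Week 8 as Section 7.3.2 requires, and then give a positive screen at the visit where a negative one is demanded.

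What is at stake is open-label follow-up. A child removed at Visit 9 contributes nothing to the 44-week extension, which serves the long-term safety part of the secondary objective (Section 5.1.2), and the reason would have nothing to do with azilsartan medoxomil. Sites that infer the exception and sites that do not would treat the same result differently. None of the discontinuation categories in Section 7.5 names a positive screen, so these withdrawals would most likely fall under the residual category and be identifiable only from its free-text field.

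**Working it through.** The plan gives no figure to reproduce here. The check is a comparison of texts, followed by simple arithmetic on the size.

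**1. Where the rule stands, and whether it carries the exception**

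| Place | Applies to | Exception stated or cited |
|---|---|---|
| Section 7.3 | Visit 9 | No |
| Section 7.3.3 | Visit 9 | No |
| Section 9.3.5 | Visit 9 | No |
| Table 9.b note (s) | Both screens | No |

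That is 0 of 4.

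**2. Whether a compliant child can be caught**

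- Sections 7.3.1 and 7.3.2 together permit a stable ADHD stimulant in the blinded phases.
- Section 7.3.2 requires that dose to be unchanged through Week 8 unless a change is medically essential. Week 8 is Visit 9, the day of the second screen.
- Criterion 19 itself gives ADHD amphetamines as a cause of a positive screen, so no outside knowledge of assays is needed to see that this can happen.

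For a child whose drug does turn the screen positive, the two rules cannot both be met. Continuing the drug fails the Visit 9 rule, and stopping it to pass breaks the stable-dose rule.

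**3. Whether removal fits the rest of the plan**

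It does not. Section 7.3.2 foresees dose adjustment of these drugs in the open-label phase. The open-label exclusion list in Section 7.3.3 has 7 entries, and none is a stimulant. Section 7.5 has 8 discontinuation categories, and none names a positive screen.

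**4. Whether the visit lists settle it**

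They point the other way. Section 9.3.1 lists the Screening test with no requirement on the result. Section 9.3.5 lists the Visit 9 test with one. A careful site could take that difference as deliberate.

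**5. Size**

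Inputs: 52 weeks of treatment, with the open-label phase starting at Week 8 (Section 2.0); at least 213 randomised (Section 6.1); 10% dropout over the double-blind and withdrawal phases (Section 13.3).

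- Ceiling per removed child: 52 − 8 = 44 weeks, and 44/52 = 84.6% of treatment time.
- Share of planned open-label follow-up per removed child, if all 213 enter: 1/213 = 0.47%.
- The same after planned dropout: 213 × 0.90 = 191.7, about 192, and 1/192 = 0.52%.

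The total is roughly 0.5% multiplied by the number of children removed. That number cannot be derived, because the documents give no rate of stimulant use, no assay panel and no age split.

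**6. Effect on the main results**

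The Week 8 blood pressure is taken at Visit 9, before open-label dosing. The primary endpoint and every Week 6 and Week 8 endpoint are therefore already collected when the rule acts. Open-label data are summarised descriptively only (Section 13.1.3).

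**The case against.** The strongest reply is that the protocol, read as a whole, already answers the question. The criterion 19 exception names no visit. Note (s) uses the unqualified requirement for Screening too, where the exception plainly applies, so in this document the bare wording already coexists with the exception. Section 7.3.2 expects users of these drugs to reach the open-label phase. It would be odd for a protocol to require a drug through Week 8 and then expel the child at Week 8 for taking it. Section 7.6 ties termination by the investigator to the Section 7.5 criteria, which do not name a positive screen. The laboratory manual, which is not available here, may say how a positive result from a prescribed drug is handled. A site in doubt can consult the medical monitor under Section 14.2.

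Most of this stands as evidence of intent, and the sponsor probably did mean the exception to carry over. It does not close the gap in the text. Criterion 19 belongs to a list that governs entry, and no sentence extends it to continuation. Section 14.2 tells investigators not to deviate except to remove an immediate hazard, so a literal reading is a safe choice for a site. Consultation case by case can still produce different outcomes for the same result.

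It is also fair to say that harm is not demonstrated. The documents do not show that every permitted stimulant would test positive, and the percentages above describe one hypothetical child.

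**Conclusion.** The point holds and is minor. All four statements of the rule omit the criterion 19 exception, and followed literally they would remove a compliant child on a permitted stimulant from up to 44 weeks of open-label treatment and safety follow-up. Each such child costs about 0.5% of planned open-label follow-up (0.47% to 0.52%), so the effect is small unless many are affected. No confirmatory result is touched.

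The conclusion assumes that at least some permitted stimulants give a positive result on the panel used, which criterion 19 implies for amphetamines, and that some sites would apply the Visit 9 wording as written. Confidence in the textual gap is high. How often it would matter in practice is unknown.

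**What to change.** In Sections 7.3, 7.3.3 and 9.3.5 and in Table 9.b note (s), add a sentence along these lines: a positive screen explained by a known physician-prescribed drug that the investigator judges is not being abused, and that is not an excluded medication, does not prevent the subject from continuing. A cross-reference to exclusion criterion 19 and Section 7.3.2 would serve equally well.

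This keeps both safeguards in the existing exception and brings the Visit 9 rule into line with the concomitant-medication rules. The cost is one sentence of protocol wording in four places. Procedures, sample size and analysis do not change.

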7.3.1 Washout/Placebo Run-in, Double-Blind and Withdrawal Phases: Excluded Medications

The following medications will be prohibited during the Washout/Run-in, DB and Withdrawal Phases. When appropriate, medications may be tapered-off gradually before double-blind treatment is initiated, but a minimum drug-free period of at least 7 days is required before randomization.

- All classes of antihypertensive drugs, including drugs that have an effect on BP but are prescribed for another indication, with the exception of concomitant medications listed in [Section 7.3.2](#).
- Lithium.
- Monoamine oxidase inhibitors.
- Tricyclic antidepressants.
- Amphetamines or their derivatives (see [Section 7.3.2](#) for exceptions).
- Dopamine agonists.

- Atypical antipsychotic agents.
- Anticonvulsants.
- Trazodone.
- Nitrates.

7.3.2 Washout/Placebo Run-in, Double-Blind and Withdrawal Phases: Concomitant Medications Allowed Conditionally

Conditional use of the following medications will be allowed in the Washout/Run-in, DB and Withdrawal Phases. These medications must be at a stable dose through the Week 8 visit (end of withdrawal phase) without changes unless absolutely medically necessary. Routine weaning and/or dose adjustments can be made during the open-label phase of the study:

- Diuretics, including loop-diuretics (eg, furosemide): Stable dose allowed if indicated for the treatment of oedema/CKD.
- Steroids: Systemic use is allowed at stable low/maintenance dose up to hydrocortisone 12 mg/m²/day (or the appropriate dose equivalent if other steroid is administered) for replacement therapy in subjects with adrenal insufficiency or other medical conditions. Immunosuppressive treatment in post renal transplant subjects or in subjects with glomerular disease with prednisolone is allowed at a maximum dose of 15 mg/m² (0.5 mg/kg) (or the appropriate dose equivalent if other steroid is administered). Doses need to be stable at least 30 days prior to Screening as mandated by inclusion criterion #8Topical and inhaled corticosteroids (eg, for treatment of asthma) are also allowed at stable maintenance doses.
- Central nervous system (CNS) stimulants: Stable dose allowed if indicated for treatment of attention deficit hyperactivity disorder.
- Nonsteroidal anti-inflammatory drugs (NSAIDs): Use of NSAIDS is allowed if not used chronically (ie, more than 3 times per week). Maximum allowed daily dose of ibuprofen is 30 mg/kg/day in 3 to 4 divided doses (total daily maximum of 2.4 g). Acetaminophen (or paracetamol) is not excluded.

For diuretics, steroids, and CNS stimulants, a stable dose is defined as no dosage change in the preceding 30 days before Screening/Visit 1.

7.3.3 Open-Label Phase: Excluded Medications

The following medications are excluded during the OL Phase of the study.

- ARBs other than AZM.
- ACE inhibitors.
- Aliskiren.
- Chronic use of NSAIDs (ie, more than 3 times per week).

CONFIDENTIAL

- Lithium.
- Monoamine oxidase inhibitors.
- Nitrates.

Results of the urine alcohol and drug screen performed at Visit 9 must be negative for the subject to continue in the study.

7.4 Diet, Fluid, Activity Control

Subjects will be encouraged to follow a healthy diet and maintain a constant food intake (including for optimal weight maintenance but not active weight loss) during the blinded phases of the study. Throughout the study, subjects should be advised to avoid foods high in sodium and to maintain good hydration. Subjects will also be instructed to maintain usual sleep habits, activity, and caffeine intake throughout the study, although excessively vigorous physical activities or contact sports should be avoided on ABPM days.

7.5 Criteria for Discontinuation or Withdrawal of a Subject

The primary reason for discontinuation or withdrawal of the subject from the study should be recorded in the electronic case report form (eCRF) using the following categories. For screen failure subjects, refer to [Section 9.1.13](#).

1. Pretreatment event (PTE) or AE. The subject has experienced a PTE or AE that requires early termination because continued participation imposes an unacceptable risk to the subject's health or the subject is unwilling to continue because of the PTE or AE. See [Section 9.1.8.1](#) for instructions regarding withdrawal and follow-up of patients with acute decreases in renal function.
2. Major protocol deviation. The discovery postrandomization that the subject failed to meet protocol entry criteria or did not adhere to protocol requirements, and continued participation poses an unacceptable risk to the subject's health.
3. Lost to follow-up. The subject did not return to the clinic and attempts to contact the subject were unsuccessful. Attempts to contact the subject must be documented.
4. Voluntary withdrawal. The subject (or subject's legally acceptable representative) wishes to withdraw from the study. The reason for withdrawal, if provided, should be recorded in the eCRF.

Note: All attempts should be made to determine the underlying reason for the withdrawal and, where possible, the primary underlying reason should be recorded (ie, withdrawal due to an AE or lack of efficacy should not be recorded in the "voluntary withdrawal" category).

5. Study termination. The sponsor, IRB, IEC, or regulatory agency terminates the study.
6. Pregnancy. The subject is found to be pregnant.

Note: If the subject is found to be pregnant, the subject must be withdrawn immediately. The procedure is described in [Section 9.1.10](#).

7. Lack of efficacy. The investigator has determined that the subject is not benefiting from investigational treatment; and, continued participation would pose an unacceptable risk to the subject.

Note: If the subject's clinic seSBP and/or seDBP is greater than 15/10 mm Hg above the 99th percentile at the site during any phase of the study, the subject should return within 48 hours for a repeat BP measurement. If BP remains elevated above this threshold at the repeat visit while the subject is receiving single-blind or double-blind treatment, the subject should be withdrawn and resume appropriate antihypertensive medication. Subjects who are receiving open-label treatment but whose blood pressure is confirmed to be elevated to greater than 15/10 mm Hg above the 99th percentile despite dose-titration and addition of other antihypertensive agents should also be withdrawn.

8. Other.

Note: The specific reasons should be recorded in the "specify" field of the eCRF.

7.6 Procedures for Discontinuation or Withdrawal of a Subject

The investigator may terminate a subject's study participation at any time during the study when the subject meets the study termination criteria described in [Section 7.5](#). In addition, a subject may discontinue his or her participation without giving a reason at any time during the study. Should a subject's participation be discontinued, the primary criterion for termination must be recorded. In addition, efforts should be made to perform all procedures scheduled for the Early Termination Visit. Discontinued or withdrawn subjects will not be replaced.

8.0 CLINICAL TRIAL MATERIAL MANAGEMENT

This section contains information regarding all medication and materials provided directly by the sponsor, and/or sourced by other means, that are required by the study protocol, including important sections describing the management of clinical trial material.

8.1 Study Medication and Materials

8.1.1 Dosage Form, Manufacturing, Packaging, and Labeling

In this protocol, the term study medication refers to all or any of the drugs defined below.

- AZM 10 mg, 20 mg, 40 mg, 80 mg, or placebo orally administered tablets.
- Overencapsulated (O/E) losartan 25 mg, 50 mg, 100 mg, or placebo orally administered capsules.

